7 STUDY CALENDAR & EVALUATIONS

Study Day [Cycle = 14 days]	Screen	Cycle 1	Cycle 2 +	Safety Follow up ¹⁴	Safety Follow up ¹⁴	Long Term Follow Up ¹⁵
	-28 days	Day 1 (± 3)	Day 1 (± 3)	30 days (±7)	90 days (±7)	Q 3 months (±14 days)
REQUIRED ASSESSMENTS						
Informed Consent/HIPAA auth.	X					
Medical History ¹	X					
Physical Exam	X	X	X	X		
Vital Signs including ECOG PS ²	X	X	X	X		
AE Assessment and Con Meds	X	X	X	X	X	
LABORATORY ASSESSMENTS						
Blood Chemistries ³	X	X ¹³	X	X		
Thyroid Function Testing ⁴	X	X ¹³	X	X		
PT/INR and aPTT	X	X ¹³	X	X		
Platelets, ANC & Hgb	X	X ¹³	X	X		
Urinalysis	-7d ⁵	X ¹³	X			
Pregnancy Test for WOCP ⁶	X	-24h	X ⁶			
DISEASE ASSESSMENT						
CT or MRI chest, abdomen/pelvis ⁷	X		X			X
CT or MRI Brain, if indicated ⁷	[X]					
TREATMENT						
Nivolumab		X	X			
Ramucirumab		X	X			
CORRELATIVE STUDIES						
CT-guided biopsy ⁸	X		X ⁸			
Whole Blood for Somatic Baseline ⁹		X				
Serum for soluble PD-L1 analysis ⁹		X	C5D1			
BANKING SAMPLES						
Whole Blood ¹⁰ - Optional		X				
Serum and Plasma ¹¹ - Optional		X		X		
Unstained Slides ¹² - Optional		X	X ¹²			
FOLLOW UP						
Survival status, additional cancer therapy						X

Footnotes:

1. Medical history to include demographics, prior treatments, radiation and surgical history. Other information obtained during the medical history includes: Smoking history to include: amount, frequency, start and stop dates of cigarette, cigar and pipe usage. A question about how the patient heard about the study. Prior genetic or biomarker testing results will be required if available.
2. Vital signs to include BP, HR, weight, height (screening) only. In addition, ECOG performance status should be obtained.
3. Blood Chemistries to include: sodium, potassium, blood urea nitrogen (BUN), serum creatinine (or GFR; see 3.1.7), calcium, albumin, ALT, AST, bilirubin, alkaline phosphatase (ALK), total protein, glucose.
4. Thyroid studies will be obtained every 3 cycles (about 6 weeks) starting with Cycle 4 (\pm 7 day window). The type of testing performed (TSH, T3 free vs direct, or T4 free vs direct) should be per local standards.
5. Within 1 week of study registration. If urine dipstick or routine analysis is $\geq 2+$, a 24-hour urine collection for protein must demonstrate < 1000 mg of protein in 24 hours to allow participation in this protocol.
6. A negative serum or urine pregnancy test is required at screening for eligibility and within 24 hours of initiation of study treatment. If the urine test cannot be confirmed as negative, a serum pregnancy test will be required. Pregnancy testing will be done every 4 weeks.
7. Appropriate scans to assess disease status will be obtained within 4 weeks of initiation of study treatment including CT or MRI of the chest, abdomen/pelvis. After that time, disease assessment will be performed every 4 cycles (8 weeks) for 6 months, then every 6 cycles (12 weeks) until disease progression for a maximum of 2 years from initiation of study treatment. A brain MRI or CT will be performed at screening for subjects with a prior history of brain metastasis or if there is suspicion of brain metastasis.
8. The subject will need to undergo a CT-guided biopsy (i.e., image-guided percutaneous lung biopsy) to obtain tumor tissue within 28 days before initiation of treatment and after 4 cycles (8 weeks) of treatment, for analysis of location and number of tumor infiltrating CD8+ cells and Granzyme B+ T cells, and PD-L1 and cytokine expression in different regions of the tumor. Biopsy to include FFPE and snap frozen tissue. See Correlative Laboratory Manual (CLM) for collection, labeling and shipping instructions.
9. Mandatory submission of whole blood for somatic baseline testing prior to treatment on C1D1. Mandatory submission of serum (soluble PD-L1) will be collected at Pre-Treatment Cycle 1 Day 1 and Pre-Treatment Cycle 5 Day 1. See CLM for collection, processing, labeling and shipping instructions.
10. Optional submission of whole blood for banking is to be collected at Pre-Treatment Cycle 1 Day 1. See CLM for collection, processing, labeling and shipping instructions.
11. Optional submission of serum and plasma for banking are to be collected at Pre-Treatment Cycle 1 Day 1 and at the D30 safety follow up visit. See CLM for collection, labeling, processing, and shipping instructions.
12. Optional submission of unstained slides for banking from the biopsy done prior to treatment C1D1 and after 4 cycles of treatment will be requested. See CLM for collection, labeling, and shipping instructions.
13. For Cycle 1 only: labs do not need to be repeated if done within 7 days of Day 1.
14. Safety Follow Up Visits: 30 days (± 7) post last dose of study treatment. For subjects with unresolved treatment related toxicity, follow as medically appropriate until resolution or stabilization. Day 90 AE and conmed assessment may be done by phone, email or other avenues as appropriate.
15. Long-term follow up: Every 3 months until 2 years from initiation of study therapy. Follow up may be accomplished by phone call, email, local physician's record. Disease assessment will be performed per physician's discretion. Results of all disease assessment should be captured. If the patient progresses, they should be followed for survival and/or initiation of anti-cancer therapy.

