6.3.2 Nivolumab Dose Delay Criteria

Adverse events (both non-serious and serious) associated with nivolumab exposure may represent an immunologic etiology. These adverse events may occur shortly after the first dose or several months after the last dose of treatment. Nivolumab must be withheld for drug-related toxicities and severe or life-threatening AEs as per Table 3 below. See Section 5.4 for supportive care guidelines, including use of corticosteroids. **NOTE:** In addition to information in the table, permanently discontinue for any severe or Grade 3 drug-related AE that recurs or any life-threatening event. Subjects with intolerable or persistent Grade 2 drug-related AE may have study medication held at physician discretion. Permanently discontinue study drug for persistent Grade 2 adverse reactions for which treatment with study drug has been held, that do not recover to Grade 0-1 within 6 weeks of the last dose unless delay beyond 6 weeks allows for prolonged steroid taper to manage toxicity. In such cases, the Sponsor Investigator must be consulted prior to re-initiating treatment.

Table 3: Nivolumab dose modification guidelines for drug-related adverse events

Toxicity	Hold Treatment For	Timing for Restarting Treatment	Discontinue Subject
Diarrhea/Colitis	Grade 2-3	Toxicity resolves to Grade 0-1	Toxicity does not resolve within 6 weeks of last dose unless delay beyond 6 weeks allows for prolonged steroid taper to manage toxicity. In such cases, the Sponsor Investigator must be consulted prior to re-initiating treatment.
	Grade 4	Permanently discontinue	Permanently discontinue
Pneumonitis	Grade 2	Toxicity resolves to Grade 0-1	Toxicity does not resolve within 6 weeks of last dose unless delay beyond 6 weeks allows for prolonged steroid taper to manage toxicity. In such cases, the Sponsor Investigator must be consulted prior to re-initiating treatment.
	Grade 3-4	Permanently discontinue	Permanently discontinue
Hepatitis	≥ Grade 2 if subject has baseline AST, ALT or total bilirubin that is within normal limits; ≥ Grade 3 if subject has baseline AST, ALT or total bilirubin within the Grade 1 toxicity range	Toxicity resolves to Grade 0-1	Toxicity does not resolve within 6 weeks of last dose unless delay beyond 6 weeks allows for prolonged steroid taper to manage toxicity. In such cases, the Sponsor Investigator must be consulted prior to re-initiating treatment.

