11.1.2 Laboratory Test Abnormalities

However, the following laboratory abnormalities should be documented and reported appropriately:

- any laboratory test result that is clinically significant or meets the definition of an SAE or Drug Induced Liver Injury (DILI)
- any laboratory abnormality that required the participant to have study drug discontinued or interrupted
- any laboratory abnormality that required the subject to receive specific corrective therapy.

Wherever possible, the clinical rather than laboratory term should be used by the reporting investigator (e.g., anemia versus low hemoglobin value).

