11.2 Adverse Event (AE) Recording

- Adverse events (AEs) will be recorded from the time of consent until 100 days after treatment discontinuation of study drugs, or until a new anti-cancer treatment starts, whichever occurs first.
- AEs will be recorded regardless of whether or not the event(s) are considered related to the study drugs.
- All AEs will be recorded in the subject's medical record and on the appropriate study specific eCRF form within the EDC system.
- All AEs considered related to study drugs will be followed until resolution to \leq Grade 1 or baseline, deemed clinically insignificant, and/or until a new anti-cancer treatment starts, whichever occurs first.

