11.3 Serious Adverse Event (SAE) Reporting

11.3.1 Site Requirements for Reporting SAEs to HCRN

- SAEs will be reported from time of signed informed consent until **100** days after discontinuation of study drug(s) or until a new anti-cancer treatment starts, whichever occurs first.
- SAEs will be reported on the SAE Submission Form and entered in the SAE tab in the EDC system **within 1 business day** of discovery of the event.
- SAEs will be reported whether or not they are related to the study drug(s).
- All SAEs will be recorded in the subject's medical record and on the appropriate study specific eCRF form within the EDC system.
- All SAEs regardless of relation to study drug will be followed until resolution to \leq Grade 1 or baseline and/or deemed clinically insignificant and/or until a new anti-cancer treatment starts, whichever occurs first.

Additionally, any serious adverse event, considered by an investigator to be related to either study drug, which is brought to the attention of the investigator at any time outside of the 100-day time period specified above, also must be reported immediately to HCRN.

The site will submit the completed SAE Submission Form to HCRN **within 1 business day** of discovery of the event. The form may be sent electronically to [contact]. The investigator is responsible for informing the IRB and/or the Regulatory Authority of the SAE as per local requirements. The original copy of the SAE Submission Form and the email correspondence must be kept within the study file at the study site.

Once the SAE has resolved, sites must submit a follow up SAE Submission Form within a reasonable timeframe to HCRN electronically to [contact].

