11.3.5 Potential Drug Induced Liver Injury (DILI)

Wherever possible, timely confirmation of initial liver-related laboratory abnormalities should occur prior to the reporting of a potential DILI event. All occurrences of potential DILIs, meeting the defined criteria, must be reported as SAEs.

Potential drug induced liver injury is defined as:

1. An elevated AST or ALT lab value that is greater than $3 \times$ the upper limit of normal, **and**,
2. an elevated total bilirubin lab value that is greater than $2 \times$ the upper limit of normal without initial findings of cholestasis (elevated serum alkaline phosphatase), **and**,
3. No other immediately apparent possible causes of aminotransferase (ALT or AST) elevation and hyperbilirubinemia, including, but not limited to, viral hepatitis, pre-existing chronic or acute liver disease, or the administration of other drug(s) known to be hepatotoxic.

DILIs that occur in any subject from the date of first dose through 100 days following discontinuation of dosing, whether or not related to Eli Lilly and Company's product and/or BMS's product, must be reported **within 1 business day** to HCRN. The site will submit a completed SAE Submission Form to HCRN **within 1 business day** of discovery of the event. The form may be sent electronically to [contact].

HCRN will report the event **within 1 business day** to Eli Lilly and Company (Attn: Global Patient Safety; [contact] or [contact]) and BMS (Attn: Global Pharmacovigilance & Epidemiology; [contact]; [contact]).

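### Adverse events are to be captured to Day 100 after discontinuation, but the last scheduled AE question is at Day 90 (±7), leaving a 3-17 day tail that is not actively sought

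*Combined protocol and SAP*

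**What the plan says.** Section 11.2 sets the recording window: "Adverse events (AEs) will be recorded from the time of consent until 100 days after treatment discontinuation of study drugs", or until new anti-cancer treatment if that comes first. Section 11.3.1 gives serious events the same limit and the same early stop. Section 11.3.5 covers potential drug-induced liver injury (DILI): "DILIs that occur in any subject from the date of first dose through 100 days following discontinuation of dosing". It states no cut-off at new therapy.

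In the Section 7 calendar, the row "AE Assessment and Con Meds" is marked at screening, at each treatment cycle, at 30 days (±7) and at 90 days (±7). It is blank under long-term follow-up, where the marked items are imaging, survival status and further cancer therapy. Footnote 14 times the 30-day safety visit from the last dose and says of the second contact: "Day 90 AE and conmed assessment may be done by phone, email or other avenues as appropriate". Footnote 15 runs long-term follow-up every 3 months until 2 years from the start of therapy, and adds: "Follow up may be accomplished by phone call, email, local physician's record". It does not mention adverse events.

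On late immune-related toxicity, Section 6.3.2 says: "These adverse events may occur shortly after the first dose or several months after the last dose of treatment".

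**The concern.** Section 11 defines what must be captured, and the calendar tells sites when to ask. Here the calendar stops before the window closes. A site that makes every scheduled contact on time has still not asked about the last days of the period for which it is responsible, and the number of days missed depends on where in the ±7 range the contact fell.

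The protocol itself expects some nivolumab events to begin months after treatment ends, so the tail cannot be presumed empty. At stake are the AE proportions in Section 12.5, which serve a secondary objective, and the completeness of late safety reporting.

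**Working it through.** The plan gives no figure for this gap, so there is none to reproduce. The check is day arithmetic and a reading of the provisions that might close the gap.

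**Inputs.** End of window: Day 100 (11.2, 11.3.1, 11.3.5). Last AE contact: Day 90 ±7, so Day 83 to Day 97 (Section 7). Planned enrollment: 35 (12.3).

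**Days with no scheduled question, if last dose and discontinuation coincide.** Gap = 100 − contact day.
- Contact on Day 97: 100 − 97 = 3 days (Days 98-100)
- Contact on Day 90: 100 − 90 = 10 days
- Contact on Day 83: 100 − 83 = 17 days (Days 84-100)

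This is 3% to 17% of the 100-day window.

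**If the two dates differ.** Section 11 counts from discontinuation, but footnote 14 counts from the last dose. The footnote states that anchor for the 30-day visit, and I assume it also applies to the 90-day contact. With discontinuation dated k days after the last dose, gap = 100 + k − contact day. The documents give no distribution for k, so these values are illustrations:
- k = 0: 3 to 17 days
- k = 14 (one cycle): 17 to 31 days
- k = 42 (the length of the 6-week nivolumab limit in Section 6.1): 45 to 59 days

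So 3-17 days is the smallest version of the gap.

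**Does another provision supply the missing question?**
- Footnote 14 follows unresolved treatment-related toxicity, and 11.2 follows related events to Grade 1 or baseline. Both concern events already known.
- Section 11.3.1 requires a related serious event to be reported if it is one "which is brought to the attention of the investigator at any time outside of the 100-day time period specified above". It depends on the event reaching the investigator, and it covers only related serious events.
- Section 6 speaks generally of AE evaluation at every study visit, but refers to Section 7 for the schedule, where long-term follow-up has no AE mark.
- Long-term follow-up ends 2 years from the start of therapy, and treatment may itself run 24 months (5.1: 52 cycles × 14 days = 728 days). A subject who completes treatment has no later scheduled contact at which the tail could come up.

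**Reach.** The stopping rule in 12.2 counts Grade 5 related toxicity in the first 4 cycles, nominally 4 × 14 = 56 days from the start of treatment. It does not depend on this contact. Nor do response, PFS or OS.

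**The case against.** The strongest reply is that soliciting and recording are different duties. Sections 11.2 and 11.3.1 bind the site whatever the calendar says, so a new non-serious event or an unrelated serious event on Day 95 must be recorded if the site hears of it. Deaths would also tend to surface through the survival checks while long-term follow-up lasts. This stands. A reader might infer that tail events fall outside the plan or are lost, and the documents do not support that. What is missing is a scheduled question.

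Three other stronger readings also fail.
- One might infer that every subject was meant to have the same 100 days of observation. For AEs and SAEs the window ends at new anti-cancer therapy, so its length differs between subjects by design.
- One might infer that missed events can only lower the reported proportions. Section 12.5 reports proportions by grade without saying how repeated events count. If each subject counts once at worst grade, missing a Grade 3 event in someone already at Grade 2 raises the Grade 2 proportion by one subject, or 1/35 = 2.9 points.
- One might infer a second conflict, because chemistries are last scheduled at the 30-day visit while DILI runs to Day 100. No passage promises testing to Day 100, and 11.1.2 already requires clinically significant results to be documented. That is missing detail, not a contradiction.

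An alternative fix is to keep Day 90 and add an AE question to the first long-term contact. This avoids any delay, but fails for subjects treated for the full 24 months, who have no long-term contact.

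**Conclusion.** The mismatch is real and small. On the assumption that last dose and discontinuation share a date, the final 3-17 days (10 nominal) of the 100-day window have no scheduled AE question. The gap is longer where discontinuation is dated later. Late events may be under-ascertained in the secondary safety tables, and scheduled ascertainment ends on different days for different subjects. In subjects who have started new anti-cancer therapy the AE and SAE window has already closed, so for them the gap matters only for potential DILI.

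The documents give no late event rate, so no number of missed events can be stated. The efficacy analyses and the stopping rule are untouched. This is a minor correction, worth making because it takes little and removes a conflict between a mandatory window and the schedule that sites follow.

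**What to change.** In the calendar heading and footnote 14, replace the 90-day (±7) contact with one at 100 days (+7), still by phone or email. A one-sided window is needed: Day 100 ±7 could fall on Day 93 and leave up to 7 days unasked.

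State one anchor, either last dose or discontinuation, and use it for this contact and for the 100-day limits in 11.2, 11.3.1 and 11.3.5. Without this, a contact 100 days after the last dose could still come before Day 100 after discontinuation.

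At the contact, ask for:
- all AEs and SAEs with onset to Day 100, or to new anti-cancer therapy if earlier, with onset dates;
- potential DILI to Day 100 regardless of new therapy, since 11.3.5 has no such cut-off.

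Events starting on Days 101-107 fall outside the window, except related serious events under 11.3.1.

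**Cost.** One heading, one footnote and aligned anchor wording in three sections. No contact, visit, blood draw or procedure is added. With the anchor dates coinciding, the contact comes 100 − 97 = 3 to 107 − 83 = 24 days later than now, so an event first learned of there is known that much later. The longest interval from the 30-day visit (earliest Day 23) grows from 97 − 23 = 74 to 107 − 23 = 84 days.

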8 CRITERIA FOR DISEASE EVALUATION

A modified version of the Response Evaluation Criteria in Solid Tumors (RECIST) 1.1 will be used in this study [35]. For the purposes of this study, subjects will be reevaluated every 4 cycles (eight weeks) for 6 months, then every 6 cycles (12 weeks) until disease progression for a maximum of 2 years from initiation of study treatment. In addition to a baseline scan, confirmatory scans should also be obtained at least four weeks following initial documentation of objective response.

8.1 Target Lesions

All measurable lesions up to a maximum of 5 lesions representative of all involved organs should be identified as target lesions and will be recorded and measured at baseline. Target lesions should be selected on the basis of their size (lesions with the longest diameter) and their suitability for accurate repetitive measurements (either by imaging techniques or clinically). Measurable lesions are defined as those that can be accurately measured in at least one dimension as 10 mm with CT scan. A lymph node must be 15 mm in short axis by CT scan in order to be considered pathologically enlarged and measurable. All measurements must be recorded in millimeters. A sum of the diameters (long diameter (LD) for all non-nodal target lesions and short axis for nodal lesions) will be calculated and reported as the baseline sum LD. The baseline sum of all diameters will be used as reference to further characterize the objective tumor response of the measurable dimension of the disease.

In subjects with pleural mesothelioma the typical mesothelial “rind” should be measured on 3 separate levels at least 2 cm apart, perpendicularly from the chest wall on a given cut. Each level should be measured in two different places. The three rind thicknesses should be recorded for a given level and compared on subsequent scans. Clear anatomic landmarks should be recorded carefully to ensure consistency from scan to scan. At least one level should have a measurement ≥ 1.5 cm. Pleural areas where the initial thickness is less than 1 cm should not be used as evaluation measurement.

A sum of the measurements of the pleural rind obtained at 3 different levels should be calculated and reported as the baseline sum LD.

These modified RECIST 1.1 criteria have been previously validated in patients with mesothelioma [35]. Response assessment using these methods has been found to be a greater clinical predictor for survival in patients with mesothelioma than a method of longest diameter to assess pleural thickness.

8.1.1 Complete Response (CR)

Disappearance of all target lesions. Changes in tumor measurements must be confirmed by repeat studies performed no less than 4 weeks after the criteria for response are first met.

8.1.2 Partial Response (PR)

At least a 30% decrease in the sum of the diameters of target lesions taking as reference the baseline sum LD. Changes in tumor measurements must be confirmed by repeat studies performed no less than 4 weeks after the criteria for response are first met.

8.1.3 Progression

At least a 20% increase in the sum of the diameters of target lesions taking as reference the smallest sum LD recorded since the treatment started or the appearance of one or more new lesions.

